Attachment 1: Definition and classification of SSI according to CDC

Surgical site infection (SSI) can be subdivided into infections of the subcutaneous tissue (superficial SSI), deep soft tissues such as fascial and muscle layers (deep SSI) and infections of organs or spaces (organ/space SSI) that occur within 30 days after surgery.

Superficial Incisional SSI	
Infection occurs within 30 days after the operation and infection involves only skin or subcutaneous tissue of the incision and at least one of the following:
 
1. Purulent drainage, with or without laboratory confirmation, from the superficial incision.2. Organisms isolated from an aseptically obtained culture of fluid or tissue from the superficial incision.3. At least one of the following signs or symptoms of infection: pain or tenderness, localized swelling, redness, or heat and superficial incision is deliberately opened by surgeon, unless incision is culture-negative.4. Diagnosis of superficial incisional SSI by the surgeon or attending physician. 
**Notes**: Do not report the following conditions as SSI:
 
1. Stitch abscess (minimal inflammation and discharge confined to the points of suture penetration).
Deep Incisional SSI	Infection occurs within 30 days after the operation and the infection appears to be related to the operation and infection involves deep soft tissues (e.g., fascial and muscle layers) of the incision and at least one of the following:

	
1. Purulent drainage from the deep incision but not from the organ/space component of the surgical site.2. A deep incision spontaneously dehisces or is deliberately opened by a surgeon when the patient has at least one of the following signs or symptoms: fever ($>38^{\circ}\text{C}$), localized pain, or tenderness, unless site is culture-negative.3. An abscess or other evidence of infection involving the deep incision is found on direct examination, during reoperation, or by histopathologic or radiologic examination.4. Diagnosis of a deep incisional SSI by a surgeon or attending physician. 
**Notes**:
 
1. Report infection that involves both superficial and deep incision sites as deep incisional SSI.2. Report an organ/space SSI that drains through the incision as a deep incisional SSI.
Organ/Space SSI	
Infection occurs within 30 days after the operation and the infection appears to be related to the operation and infection involves any part of the anatomy (e.g., organs or spaces), other than the incision, which was opened or manipulated during an operation and at least one of the following:
 
1. Purulent drainage from a drain that is placed through a stab wound into the organ/space.2. Organisms isolated from an aseptically obtained culture of fluid or tissue in the organ/space.

	
3. An abscess or other evidence of infection involving the organ/space that is found on direct examination, during reoperation, or by histopathologic or radiologic examination.
 
4. Diagnosis of an organ/space SSI by a surgeon or attending physician.

--	--

Attachment 2: ASA Classification Criteria

It refers to the six levels into which patients are classified by the American Society of Anesthesiologists (ASA) prior to anesthesia based on their physical condition and risk to surgery.

classification	condition
Level I	Physical health, good development and nutrition, and normal functioning of organs.
Level II	In addition to surgical disease, there is mild coexisting disease with sound functional compensation.
Level III	Coexisting conditions are severe and physical activity is limited, but can still manage daily activities.
Level IV	Severe coexisting conditions, loss of ability to perform daily activities, and frequent life-threatening situations.
Level V	Dying patients who have difficulty sustaining life for 24 hours, with or without surgery.
Level VI	Confirmed brain death and his organs are intended for organ transplantation.

Attachment 3: ECOG Physical Fitness Assessment Criteria

Physical condition	Grading
Normal activity	0
Mild symptoms, comfortable living, able to do light physical activities	1
Can withstand the symptoms of the tumor and take care of one's own life, but not spend more than 50% of the time in bed during the day	2
The symptoms are severe. You spend more than 50% of your time in bed during the day, but you can still get up and stand, so you can take care of yourself for part of your life	3
Sick and unable to stay bedridden	4
Death	5

Attachment 4: Postoperative Complications Clavien-Dindo System Grading

Grading	Definition	
I	There are complications of unnecessary medication, surgery, laparoscopic, and reflex intervention after surgery, but they include medications for antiemetics, fever-reducing drugs, pain relievers, diuretics, dielectrics, and physiotherapy, as well as incision infections opening at the bedside;	
II	Patients requiring medication not including phase 1 medication, incisional infections require antibiotic treatment, blood transfusions, and parenteral nutrition included	
III.	Surgical, laparoscopic, and interventional radiological treatment is required	
	IIIa	Does not require general anesthesia
	IIIb	General anesthesia required
IV	Life-threatening complications (including central nervous system complications) that require IC (intermittent monitoring) or ICU treatment	
	iVa	Insufficiency of one organ (including dialysis)
	ivB	multiple organ dysfunction
V	Death	

Attachment 5: TNM Stages of Colon Cancer (AJCC, 8th Edition, 2018)

Primary tumors:

Tx: the primary tumor cannot be evaluated;

T0: no evidence of primary tumor;

Tis: Carcinoma in situ, intramucosal cancer (the tumor invades the lamina propria of the mucosa but does not break through the myofascial layer);

T1: The tumor invades the submucosal layer (the tumor invades the submucosal layer but does not involve the intrinsic muscle layer);

T2: the tumor invades the intrinsic muscle layer;

T3: the tumor penetrates the intrinsic muscle layer to the peri-colorectal tissue;

T4: the tumor invades the sublayer of the peritoneum or invades or adheres to nearby organs or structures;

T4a: Tumor penetrates the mesenteric peritoneum (including intestinal perforation at the tumor site visible to the naked eye, and continuous infiltration of the tumor through the inflamed area to the surface of the peritoneum layer);

T4b: Tumor directly invades or attaches to neighboring organs or structures.

regional lymph nodes (N)

Nx: regional lymph nodes cannot be evaluated;

N0: no regional lymph node metastasis;

N1: There are 1-3 regional lymph node metastases (tumor diameter in the lymph nodes is greater than 0.2 mm), or no regional lymph node metastasis, but there are any number of tumor nodules;

N1a: there is 1 regional lymph node metastasis;

N1b: There are 2-3 regional lymph node metastases;

N1c: no regional lymph node metastasis, but tumor nodules in subserous, mesenteric, or peri-peritoneal tissues;

N2: There are 4 or more regional lymph node metastases;

N2a: There are 4-6 regional lymph node metastases;

N2b: There are more than 7 regional lymph node metastases.

Distant Metastasis (M)

Mx: distant transfers cannot be evaluated;

M0: no distant metastasis on imaging, that is, there is no evidence of metastatic tumors in distant sites and organs (this classification should not be determined by pathologists);

M1: the presence of metastases in one or more distal parts, organs, or peritoneum;

M1a: distant metastases are limited to a single distant site or organ, but there is no peritoneal metastasis;

M1b: Distal metastases distributed to two or more distant sites or organs, no peritoneal metastases;

M1c: Peritoneal metastases, with or without other site or organ metastases.

		N0	N1/N1c	N2a	N2b
Tis	0				
T1		I	IIIA	IIIA	IIIB
T2		I	IIIA	IIIB	IIIB
T3		IIA	IIIB	IIIB	IIIC
T4a		IIB	IIIB	IIIC	IIIC
T4b		IIC	IIIC	IIIC	IIIC
M1a		IVA	IVA	IVA	IVA
M1b		IVB	IVB	IVB	IVB
M1c		IVC	IVC	IVC	IVC

Attachment 6: The VAS pain score

It is a straight line about 10 centimeters long. One end of the line is marked as "0", representing no pain, and the other end is marked as "10", representing the most severe pain imaginable. There are no other scale marks on the line, maintaining a simple visual presentation.

Self - assessment by the Patient: The patient marks a point on the line according to his or her current pain experience to represent the degree of pain. This process is completely completed by the patient independently to fully reflect his or her subjective pain experience. For example, if the patient feels mild pain, he or she may mark a point closer to the "0" end; if the pain is very severe, the mark will be closer to the "10" end.

Degree of Pain	VAS Score Range	Description
No Pain - Mild Pain	0 - 3 points	A score of 0 represents no pain at all; a score of 1 - 3 indicates mild pain, which has a relatively minor impact on daily life and generally does not require strong painkillers.
Moderate Pain	4 - 6 points	The pain begins to have a certain impact on daily life, intensifies during daily activities, and may require relief measures such as rest and the use of over-the-counter painkillers.
Severe Pain	7 - 10 points	Unbearable pain that has a severe impact on the quality of life, greatly interfering with daily activities, sleep, and emotions, and requires strong painkillers.

Attachment 7 Completeness of Specimens

Grading	Descriptions
Mesocolic plane	Smooth intact mesocolic excision.
Intramesocolic plane	The excision disrupts the mesocolon but do not reach down to the muscularis propria.
Muscularis propria plane	The excision disrupts the mesocolon and exposed the muscularis propria.

CSP amendments summary

	Amendments in Version 2.0
Title	Change the title to "A Multicenter Randomized Clinical Trial Comparing Surgical Site Infection after Intracorporeal Anastomosis and Extracorporeal Anastomosis for Left Colon Cancer (STARS)"
Exclusion criteria	Change "planned synchronous abdominal organ resections;" to "Patients who need to undergo combined organ resection or robot-assisted colectomy".
	Change "metastatic or multiple carcinoma" to "Have a history of malignant colorectal tumor or have metastatic or multiple carcinoma".
	Add "Patients who are receiving preoperative neoadjuvant therapy."
	Add "ASA grade \geq IV and/or ECOG performance status score > 2".
	Add "Patients with other clinical and laboratory conditions that are considered by researchers as inappropriate for participating in this trial."
	Delete " end-to-end anastomosis."
Exit criteria	Delete "Serious adverse events occurred preoperatively (according to the Common Terminology Criteria for Adverse Events, CTCAE version 5.0). "
	Add "Patients with other non-tumor diseases that prevent them from continuing to receive this treatment regimen."
	Add "Patients who request to withdraw from this study cohort for various reasons after being enrolled in the study, or who cannot complete the study plan and follow-up for various reasons."
Experimental Group Procedure	Add a statement: "Note that only these three anastomotic methods are allowed in intracorporeal anastomosis. If the anastomosis was completed by inserting the circular stapler through the anus after patients were assigned to the IA group, it is considered a conversion to EA. This is because the surgeons had to make an incision and insert the circular stapler anvil into the proximal colon with the abdomen open. In these cases, the anastomosis was not completed under laparoscopy."
Control Group Procedures	Add a statement: "The method of anastomosis is at the surgeon's discretion. A side-to-side anastomosis (including antiperistaltic, isoperistaltic, or overlapping anastomosis) is recommended. Side-to-end or end-to-end anastomosis (sewn by hand or by inserting a circular stapler through the anus or proximal colon) is also allowed".
	Add figures and figure legends to explain the details of side-to-end anastomosis and end-to-end anastomosis
Analytical population	Add as-treated analysis set
Primary endpoint analysis	Add univariable analysis and multivariable analysis of SSI in as-treated population.
	Amendments in Version 2.1
Method for determining sample size	Re-estimate the sample size

Statistical analysis plan (SAP)

SAP version 1.0 (2023.12.05)

TABLE OF CONTENTS

1 Introduction.....	3
2 Study design and objectives	3
3 Sample size.....	3
4 Statistical methods	4
4.1 General calculation rules.....	4
4.2 Analysis populations.....	5
4.2.1 Modified intention-to-treat (mITT) population	5
4.2.2 Per-protocol (PP) population	5
4.2.3 As-treated (AT) population	5
4.3 Analysis of endpoints.....	5
4.4 Baseline Characteristics.....	6
4.5 Primary endpoint.....	7
4.6 Secondary endpoints	8
4.7 Subgroup analysis	9
5 Missing data.....	10
6 Interim analyses	10
7 Timing of analysis	10
Reference	10

LIST OF ABBREVIATIONS

SSI	Surgical site infection
IA	Intracorporeal anastomosis
EA	Extracorporeal anastomosis
SAP	Statistical analysis plan
mITT	Modified intention-to-treat
PP	Per-protocol
AT	As-treated
CI	Confidence intervals
ORs	Odds ratios
HR	Hazard ratio
DFS	Disease-free survival
OS	Overall survival
VAS	Visual analog score

1 Introduction

The STARS trial is a multicenter, randomized, single-blind, non-inferiority study designed to compare the incidence of surgical site infection (SSI) following intracorporeal anastomosis (IA) versus extracorporeal anastomosis (EA) in patients undergoing surgery for left colon cancer. The primary objective of this trial is to determine whether IA is non-inferior to EA in terms of SSI rates within 30 postoperative days. While the aims, hypotheses, and design of the STARS trial have been detailed elsewhere, this statistical analysis plan (SAP) will focus on the forthcoming analysis and presentation of the trial data. This SAP is conducted based on the study protocol version 2.1. The comprehensive study design, including the primary and secondary endpoints, along with the methods for determining sample size and the approach to data management, are integral to the SAP and are critical for understanding the trial's methodology and interpretation of results.

2 Study design and objectives

This is a prospective, multicenter, non-inferiority, two-arm, single-blind, randomized controlled study. The study aims to investigate the effects of intracorporeal anastomosis and extracorporeal anastomosis in laparoscopic-assisted radical left hemicolectomy on surgical site infection. It also examines the difference in postoperative recovery, safety, oncology outcomes and survival. The trial was prospectively registered in clinicaltrial.gov (NCT04201717) and the study protocol (version 1.0) has been previously published,(1) and minor revisions has been made in study protocol version 2.0 and version 2.1. Details of exclusion criteria and study treatments can be found in study protocol version 2.1.

3 Sample size

The sample size is determined based on the rate of SSI. Based on our multicenter retrospective data,(2) we estimated the incidence of overall SSI following EA in laparoscopic left hemicolectomy stands at 13.3%, while the incidence of SSI after IA is 8.0%. When there is an absolute risk difference in the SSI rate of more than 5%

within 30 days after surgery, IA is regarded as inferior to EA. Consequently, the sample size for this study is calculated based on non-inferiority, taking into account an absolute risk difference of 5%, a one-sided level of significance of 0.025, a ratio of 1:1, a power of 0.80, and a 20% drop-out rate. In total, 350 patients are required for this study, with 175 patients in the IA group and an equal number of 175 patients in the EA group.

4 Statistical methods

4.1 General calculation rules

All statistical tests were 2-sided, and statistical significance was set at $P < 0.05$. All statistical analyses were performed using R or SPSS. P-values will be quoted to three decimal places. Confidence intervals (CI) will be two-sided and 95%. CI will also be quoted to one decimal place.

Categorical variables will be reported as frequencies and percentages. Percentages will be quoted to one decimal place. Chi-square tests in contingency tables will be replaced by Fisher's exact tests if any expected cell frequency is less than five.

Absolute risk differences and the corresponding 95% CI will be calculated.

Continuous data with normal distribution were presented as mean (standard deviation) and analyzed by Student's t-test. Continuous variables with non-normal distribution were reported as medians (quartile) and compared using the Mann-Whitney U test. Hodges-Lehmann method will be used to calculate the difference in median and the corresponding 95% CI. Data will be quoted to one decimal place.

Survival data between two groups will be compared using a two-sided log-rank test stratified by pathological TNM (0–I, II, III) and age (≤ 65 years and > 65 years). The hazard ratio (HR) for disease recurrence or death will be estimated using the stratified Cox proportional hazards model, including strata of pathological TNM (0–I, II, III) and age (≤ 65 years and > 65 years). The 95% confidence interval for the HR will be constructed. Results from an unstratified analysis will also be provided. The Kaplan-

Meier methodology will be applied to estimate the median disease-free survival (DFS) and overall survival (OS) for each treatment arm. Kaplan-Meier curves will be developed.

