3.2.2 Secondary endpoint and its definitions

The secondary outcomes included:

(1) Operating time: It is defined as the period from cutting the skin to suturing the skin or doing enterostomy. It is measured in minutes.

(2) Total blood loss during operation: It is defined as the blood loss during operation and is measured in milliliters.

(3) Conversion to open surgery: It is defined as an abdominal incision larger than that necessary for specimen extraction.

(4) Postoperative complications: Postoperative complications are investigated within 30 days after an operation. It includes fever of unknown origin, bowel obstruction, anastomotic

leakage, SSI, other incisional complications, respiratory complications, urinary complications, cardiovascular and cerebrovascular complications, diarrhea, chylous fistula, intraperitoneal hemorrhage, digestive hemorrhage, gastroparesis, and others (including bacteremia, cholecystitis, ion discharge, pancreatitis, and mental and behavioral abnormalities). Complications are graded according to the Clavien–Dindo classification (17). The diagnosis of anastomotic leakage is based on the patient's postoperative clinical symptoms, signs of abdominal infection, or drainage properties and is confirmed by imaging (angiography or computed tomography) or secondary surgery. Postoperative intraperitoneal/digestive hemorrhage is defined as bloody drainage/bloody stool > 100 mL in 1 h or evidence of hemorrhage on CT, endoscopy, or angiography. The respiratory complications include pulmonary complications or pleural effusion. Urinary complications include infections, retention, and leakage.

(5) Completeness of specimens: It is evaluated according to the West classification.(18) The resected specimens will be classified into three groups according to the plane of dissection: mesocolic plane, intramesocolic plane, and muscularis propria plane

(6) Number of lymph nodes dissected: The number of lymph nodes in the mesentery will be calculated. Additionally, the metastatic lymph nodes will be counted. The pathological TNM staging was performed according to the American Joint Committee on Cancer (AJCC) Cancer Staging Manual, 8th edition.

(7) Postoperative recovery: Postoperative recovery information includes time to first flatus, time to first defecation, time to start food intake, and postoperative hospital stay. These are measured in days.

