4.4 Baseline Characteristics

The following baseline characteristics will be presented in mITT, PP and AT population:

- Sex, categorical variable;
- Age, continuous variable, measured in years;
- Body Mass Index, continuous variable, measured in kg/m²;
- American Society of Anesthesiologists grading, categorical variable
- Eastern Cooperative Oncology Group performance status score, categorical variable;
- Tumor site, categorical variable, classified as distal transverse colon (distal 1/2 of transverse colon), splenic flexure of colon (junction of transverse colon and descending colon), descending colon (descending colon and the junction of sigmoid colon and descending colon), and proximal sigmoid colon (proximal 1/3 of sigmoid colon);
- NRS2002 score, continuous variable, measured in points
- Parenteral prophylactic antibiotics, categorical variable;
- Mechanical bowel preparation, categorical variable;
- Oral antibiotic bowel preparation, categorical variable;
- Postoperative antibiotic use time, categorical variable, divide by ≥ 3 days and < 3 days;
- Clinical T stage, categorical variable;
- Clinical N stage, categorical variable;
- Clinical TNM stage, categorical variable;

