4.6 Secondary endpoints

The secondary endpoints will be compared between groups in the mITT population, PP population, and AT population.

- Operating time, continuous variable, measured in minutes;
- Total blood loss during operation, continuous variable, measured in milliliters;
- Conversion to open surgery, categorical variable;
- Postoperative complications, categorical variable. It will be analyzed according to the overall occurrence. The occurrence of its subtype (anastomotic leakage, bowel obstruction, etc.) will also be analyzed. Additionally, Clavien–Dindo classification will be analyzed (\leq grade II, \geq grade III). (3)
- Completeness of specimens, categorical variable. It is evaluated according to the West classification (mesocolic plane, intramesocolic plane, and muscularis propria plane).(4)
- Number of lymph nodes dissected, continuous variable.
- The pathological TNM stage (as per the American Joint Committee on Cancer

Cancer Staging Manual, 8th edition), categorical variable. The T stage, N stage, and TNM stage will be analyzed separately.

- Postoperative recovery, continuous variable. It includes the time to first flatus, the time to first defecation, the time to start food intake, and the postoperative hospital stay. Additionally, the time to first ambulation and the time to remove the abdominal drainage tube, which are not included in the study protocol's design, will also be analyzed. These are measured in days.
- Length of incision, continuous variable. It is measured in millimeters.
- Visual analog score (VAS) of pain, it will be analyzed as categorical variable: no to mild pain (0–3 points); moderate pain (4–6 points), and severe pain (7–10 points).
- 3-year DFS: DFS is defined as the time from randomization until the occurrence of local recurrence, distant metastasis, or death from the tumor, whichever comes first. It is measured in months. For patients who are lost to follow-up, DFS will be censored at the time of the last available tumor assessment before the missing assessments.
- 5-year OS: OS was defined as the time from randomization to death due to any cause. It is measured in months. For patients lost to follow-up, OS will be censored at the time of the last available follow-up prior to the missing assessments.

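### The DFS and OS analyses are stratified by pathological TNM, a post-randomisation variable that the SAP also compares as an outcome, and the SAP does not say whether the stratified or the unstratified result takes precedence

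*Combined protocol and SAP*

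**What the plan says.** SAP 4.1 sets the test: survival in the two arms is "compared using a two-sided log-rank test stratified by pathological TNM" (0–I, II, III) and age (65 years or younger versus older). The HR comes from a "stratified Cox proportional hazards model, including strata of pathological TNM (0–I, II, III) and age", with the same age split. The same paragraph adds: "Results from an unstratified analysis will also be provided". It does not say which of the two results governs.

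SAP 4.6 puts pathological stage among the secondary endpoints compared between arms: "The T stage, N stage, and TNM stage will be analyzed separately". It also lists "Number of lymph nodes dissected, continuous variable". Protocol 2.1 section 3.2.2 places staging under the lymph-node outcome: "Additionally, the metastatic lymph nodes will be counted. The pathological TNM staging was performed according to the American Joint Committee on Cancer".

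Protocol 7.4 aims for randomisation on the day before surgery, and SAP 4.6 measures DFS and OS from randomisation. SAP 4.4 lists a stage variable among the baseline characteristics, "Clinical TNM stage, categorical variable", but no survival analysis uses it. Protocol 12.3.2 says only that the Cox model adjusts for relevant risk factors, without naming them. Protocol 6.1 describes 1:1 random codes and names no stratification factor.

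**The concern.** A stratum in a randomised comparison should be fixed before treatment, so that within each stratum the arms differ only by chance. Pathological TNM is read from the specimen that the randomised operation produces. The number of nodes retrieved affects whether a patient is recorded as node-negative (stage II) or node-positive (stage III).

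If one arm yields fewer nodes, some of its true stage III patients are recorded as stage II. Recorded stage II in that arm then contains higher-risk patients than recorded stage II in the other arm. The stratified log-rank test and HR read this difference in mix as a treatment effect. A larger sample does not remove the bias.

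There is a conceivable route: marginal vessels and mesentery are divided inside the body in the IA arm (protocol 7.2.1) and outside it in the EA arm (7.2.2). At stake is the survival comparison that serves the protocol's secondary, oncological purpose.

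**Working it through.** **The plan's own figure.** The documents state no HR, event count or power for DFS or OS. The only design figure is the SSI sample size. It reproduces: (0.133×0.867 + 0.080×0.920)×(1.960+0.842)²/(0.05+0.053)² = 139.8, so 140 per arm; 140/(1−0.20) = 175 per arm, 350 in total. It is used below only to judge precision.

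**Order of events in the documents.** Clinical stage (needed for eligibility) → randomisation, when the DFS and OS clocks start → operation → specimen → pathological stage. The stratum is therefore fixed after the clock starts and after the randomised treatment.

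**Size of the possible bias.** The inputs below are assumptions; the documents give none of them.
- True stage mix 0–I/II/III: 25/40/35% in both arms.
- Yearly hazards by true stage: set A 0.02/0.05/0.12, set B 0.02/0.06/0.20.
- Five years of follow-up and a true HR of 1.
- In one arm only, a share m of true stage III is recorded as stage II.
- The age stratum is left out because it does not bear on this mechanism.

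Method: solve the large-sample Cox score equation for the log HR b, summed over recorded strata s,

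Σₛ ∫ [e₁ₛ(t) − {n₁ₛ(t)eᵇ/(n₁ₛ(t)eᵇ + n₀ₛ(t))}·(e₁ₛ(t)+e₀ₛ(t))] dt = 0,

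where n is the expected number at risk and e the expected event rate. The HR is for the correctly staged arm versus the under-staged arm.

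| m | Stratified HR, set A | Stratified HR, set B | Unstratified HR |
|---|---|---|---|
| 0% | 1.000 | 1.000 | 1.00 |
| 5% | 0.983 | 0.978 | 1.00 |
| 10% | 0.968 | 0.958 | 1.00 |
| 20% | 0.938 | 0.920 | 1.00 |
| 30% | 0.911 | 0.884 | 1.00 |

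**Where it arises.** Within recorded stages 0–I and III the HR stays at 1.000, because the migrating patients are a random share of stage III. Only stage II is distorted. For set A at m = 10%, the starting stage II hazard in the under-staged arm is (0.40×0.05 + 0.035×0.12)/0.435 = 0.0556, against 0.05 in the other arm.

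**Against sampling error.** Five-year event probability:
- Set A: 0.25×0.0952 + 0.40×0.2212 + 0.35×0.4512 = 0.270, about 95 events in 350 patients. SE(log HR) ≈ 2/√94.6 = 0.206.
- Set B: 0.25×0.0952 + 0.40×0.2592 + 0.35×0.6321 = 0.349, about 122 events. SE ≈ 2/√122.0 = 0.181.

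Type I error is Φ(−1.96+δ) + Φ(−1.96−δ), with δ = |log HR|/SE.

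| m | δ, set A | δ, set B | Two-sided type I error |
|---|---|---|---|
| 10% | 0.16 | 0.24 | 5.3–5.7% |
| 20% | 0.31 | 0.46 | 6.1–7.5% |

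With 280 analysed patients (20% lost), δ is smaller: 0.14–0.21 at 10% and 0.28–0.41 at 20%.

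**The case against.** The case on the other side is substantial.

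- **The unstratified analysis is already planned.** In the working above it stays at 1.00 in every scenario, so distortion would tend to show as a gap between two reported results. This stands and limits the harm. It does not settle which result counts if they disagree.
- **The route to differential staging is thin.** Protocol 7.2 requires complete mesocolic excision and central vascular ligation in both arms, and both arms mark a 10-cm resection margin. The randomised contrast is how the anastomosis is made. Listing node count as an endpoint shows that it will be checked, not that a difference is expected. This stands too.
- **The effect is small.** Even the 20% scenarios shift the estimate by less than half a standard error, on secondary endpoints with no stated survival hypothesis or power.
- **Pathological stage is the stronger prognostic factor.** Stratifying by it gains precision, and nothing in the randomisation requires a clinical-stage stratum. This is true, but the precision is bought by conditioning on a possible effect of treatment.

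A reader might infer that the arm with the better nodal harvest would look better in every stage. The working does not support that: only stage II moves. A reader might also call the stratified result the leading survival analysis; the SAP names it first but gives it no such status.

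**Conclusion.** The point holds as a conditional one. The survival stratum is measured after randomisation and is itself a secondary endpoint, so the stratified DFS and OS comparison is protected by randomisation only if staging does not differ by arm. The documents do not show that it will differ, and without a difference the bias is zero.

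If it does, the stratified HR under no true effect is about 0.96–0.97 at 10% one-arm under-staging and about 0.92–0.94 at 20%. These values rest on the assumed stage mix, hazards, follow-up and random migration. They are small beside a standard error of about 0.18–0.21, so a reader should not infer that the plan is likely to produce a false survival finding. The missing statement of precedence is a gap whatever the size of the bias.

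Severity is low to moderate: DFS and OS are secondary, and the primary SSI analysis is unadjusted (SAP 4.3) and unaffected.

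**What to change.** In SAP 4.1:

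1. Replace pathological TNM with clinical TNM stage in both the stratified log-rank test and the stratified Cox model, and keep age. Define the clinical categories; with eligibility at cT1–4a, N0–2, M0, stages I, II and III would serve.
2. State that this is the main survival analysis and that the planned unstratified analysis supports it.
3. Label any result stratified by pathological TNM as a sensitivity analysis, to be read alongside the between-arm comparison of node count and pathological stage.

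The cost is a short edit to one paragraph and a small loss of precision, because clinical stage is the weaker prognostic factor. No new data are needed, and the sample size stays at 350. The survival analysis comes after all patients complete five years of follow-up (SAP section 7), later than the primary analysis.
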